2.5 Clinical Studies

MIV-150 Oral Formulation Trials

MIV-150 was studied in 4 Phase 1 clinical trials (see Table 8 below) in men using different oral formulations and dose levels by Chiron Corporation. There were no SAEs reported in association with MIV-150 oral administration. None of these 4 studies achieved the target systemic trough concentration of greater than 120 ng/mL considered necessary for antiviral efficacy. 19 In the Chiron clinical development program, MIV-150 was given to over 60 volunteers in these 4 studies using micronized and nanocrystal dispersion (NCD) formulations. MIV-150 was well-tolerated in 2 single and 2 multiple oral dose studies with doses of 200 to 1600 mg per day. Relative bioavailability was greater for the NCD than the micronized suspension. Treatment-emergent clinical events related to study drug were mild and transitory, and consisted of somnolence, fatigue, and anorexia. After administration of NCD, the absorption of MIV-150 was rapid, with C_{max} occurring within 2 hours. After attaining C_{max}, plasma concentrations declined rapidly in an apparent biphasic manner, and 12-hour trough levels were lower than expected. To achieve higher trough levels, 2 controlled-release (CR) formulations of MIV-150 with zero-order (CR01) and first-order (CR02) release kinetics were studied (MIV-102; Table 8). Although there was no significant difference between the 2 formulations, the extent of exposure was up to 17% greater for CR01 than CR02. CR01 was then selected for a multiple dose Phase 1 study (MIV-103, Table 8). Mean trough levels of approximately 48.4 + 29 and 100 + 70 ng/mL were achieved with 800 mg BID and 400 mg TID regimens, respectively. The AUC(0-∞) and Cmax values increased in a less than dose proportional manner over the ascending dose levels in all 4 trials, indicating that absorption is dissolution rate limited. Neither the CR01 nor CR02 formulations provided a superior profile to the parent NCD formulation.

Additional trial details appear below in Table 8 and in the IB.19

Table 8: Summary of Completed Clinical Studies with MIV-150

Study	Study Name	Population (N)	(Oral) Dose	Findings:	Findings:

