The Population Council Protocol #558 proceeded upon satisfactory safety and PK assessments from the run-in trial.¹⁷ In this Phase 1, double-blind, parallel, placebocontrolled, randomized trial with 20 HIV-seronegative women at a US site, participants were randomized (4:1) to apply vaginally 4 mL PC-1005 C (the same formulation, based on the PC-1005 specifications for Phase 1 study product, to be used in MTN-037) or placebo once a day for 14 days. 17 Safety, PK, pharmacodynamics, and acceptability were evaluated. All PK sampling followed directly observed dose administration. Participants were randomized (1:1) to a final PK/PD assessment that included collection of CVL for antiviral activity, at either 4 or 24 hours after the Day 14 dose. All 7 CVLs collected 4 hours after the Day 14 dose showed measurable anti-HPV activity in cell-based assays. 17 Participants (n=20) ranged from 19-44 years old; 52% were Black or African American. A total of 23 treatment emergent adverse events (TEAEs) occurred during the trial. Adverse events were primarily mild and/or unrelated and were comparable between groups; the majority of AEs were DAIDS Grade 1 (11, PC-1005; 2, placebo) or Grade 2 (4, PC-1005, 1, placebo). There were no Grade 3 or 4 AEs and no participant discontinued product because of AEs. AEs designated as related by the study investigator included metrorrhagia, vaginal discharge, vulvovaginal pruritus, abdominal discomfort, constipation, and urinary tract infection in the PC-1005 group; and uterine spasm (cramps) in both groups. No significant histopathologic changes in cervical or vaginal biopsies were observed in any of the 17 women who completed the randomized period. Median peak (C_{max}) MIV-150 concentrations ranged from 75 to 114 pg/mL and no accumulation of drug concentration with time was seen. Median time to peak concentration (T_{max}) ranged from 3-5 hours at different periods of the study (overall range 2-12 hours). Median half-life ranged from 3.9-5.5 hours. Plasma zinc levels were unchanged from baseline and were within the normal range (60-130 µg/dL). 17 All (7/7) CVLs collected 4h post-dose demonstrated antiviral (HIV, HPV) activity. High baseline CVL anti-HSV-2 activity precluded assessment of post-dose activity. Among those completing the trial (13/17, PC-1005; 3/3, placebo), 11/17 reported liking the gel overall; 7 recommended reducing the volume.

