#### Rectal Fluid and Rectal Tissue Concentrations

For rectal fluid and rectal tissue, the concentration-time profile will consist of data from different participants at different sampling time points. Individual participant PK parameters will not be calculated for concentration data from rectal fluid and rectal tissue since data were not collected at each time point for each participant.

Displays of rectal fluid and rectal tissue concentration data include:

- For each matrix (RF, RT), tables summarizing the distribution of concentrations at each sampling time point for each dose/volume (3 tables per matrix, or 1 table per matrix with a column for each dose/volume).
- For each matrix (RF, RT), scatter plots of MIV-150 concentration-time data for each dose/volume (3 plots per matrix, or 1 panel per matrix with 3 plots (1 for each dose/volume)).
- For each matrix (RF, RT), plots of mean/median concentration at each time point (with 95% C.I.) for each dose/volume (3 plots per matrix, or 1 panel per matrix with 3 plots (1 for each dose/volume)).
- For each matrix (RF, RT), tables of PK parameters calculated from mean/median concentrations at each sampling time point for each dose/volume (3 tables per matrix).

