# The PK parameters are:

Cmax Maximum observed MIV-150 concentration.

Clast Last observed MIV-150 concentration.

tmax Time of occurrence for Cmax

AUC0-t Area under the MIV-150 concentration-time curve to the time of the last measurable

concentration.

AUC0-∞ Area under the MIV-150 concentration-time curve to infinite time. Equal to AUC0-t plus

 $AUC_{t-\infty} = (C_{last} / k_e).$ 

ke Terminal elimination rate constant.

 $t_{1/2}$  Half-life of drug elimination in the terminal phase.

%AUCex Percentage of AUC0-∞ obtained by extrapolation, calculated as [(Clast / ke) / AUC0-∞ \*100]

The time, in hours, to each sample collection time is calculated from the time of dose insertion. The area under the curve (AUC) is calculated for each participant using the trapezoidal method from the time of dose insertion to the time of the last sample collection (AUC $_{0-t}$ ), typically at 24h or 48h.

Concentrations after  $C_{max}$  are used to determine the terminal elimination rate constant ( $k_e$ ) and associated half-life of MIV-150 elimination in the terminal phase ( $t_{1/2}$ ), when at least three such concentration values are available, according to the following formulas:

$$k_e = \ln (C_1/C_2) / (t_2 - t_1)$$
  
 $t_{1/2} = \ln(2) / k_e$ 

where In is the natural logarithm,  $C_1$  is the first MIV-150 concentration value in the elimination phase after  $C_{max}$ ,  $C_2$  is the last MIV-150 concentration in the elimination phase after  $C_{max}$ , and  $t_1$  and  $t_2$  are the time (hours) of the first and last MIV-150 concentration values in the elimination phase after  $C_{max}$ , respectively, as measured from the time of dose insertion.

The area under the plasma MIV-150 concentration-time curve to infinite time (AUC0-∞) is calculated by extrapolating the area of the curve after the last observed plasma MIV-150 concentration ( $C_{last}$ ) by dividing  $C_{last}$  by the terminal elimination rate constant ( $k_e$ ) and adding the result to AUC0-t. The percentage of AUC0-∞ obtained by extrapolation (%AUCex) is calculated as [(AUCt-∞ / AUC0-∞)\*100].

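### The terminal rate constant is a two-point slope over an undefined elimination phase, so half-life and AUC0-inf may be off in either direction and would mostly describe early-peaking profiles

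*SAP*

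**What the plan says.** SAP Section 9.2, in the list of PK parameters, names ke the terminal elimination rate constant and t1/2 the half-life of the terminal phase. Both are obtained from concentrations after Cmax, "when at least three such concentration values are available". The formula is ke = ln(C1/C2)/(t2 − t1). C1 "is the first MIV-150 concentration value in the elimination phase after" Cmax, and C2 "is the last MIV-150 concentration in the elimination phase after" Cmax. The elimination phase is not defined further. There is no regression, no rule for choosing points, no fit statistic and no limit on extrapolation. The same ke gives t1/2, AUC0-inf and %AUCex.

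SAP Section 9 schedules plasma before dosing and at 1, 2, 3, 4, 5-6 and 24 h. SAP Section 2.3.1 and Protocol Section 7.4.3 add blood at 48 h after one volume per participant. SAP Section 9.1 treats values below the limit of quantitation (BLOQ) at the end of a profile as missing, and no limit (LLOQ) is stated.

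For rectal fluid and tissue, SAP Section 9.2 says that "the concentration-time profile will consist of data from different participants at different sampling time points". It drops individual parameters for that reason, but still tabulates the same parameters from the mean or median curve. SAP Section 10.2 repeats this for vaginal fluid.

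**The concern.** The label and the calculation do not match. A three-value minimum normally protects a fitted slope; here the middle values are required and then ignored. A slope that starts just after the peak mixes absorption or distribution with elimination. The protocol gives a reason to think of this: after the oral nanocrystal formulation, "plasma concentrations declined rapidly in an apparent biphasic manner" (Protocol Section 2.5), and Table 8 there lists biphasic disposition with a 3-24 h half-life for study MIV-103b.

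Three things are at stake in the PK tables: a half-life labelled terminal that may not be; an AUC0-inf whose tail depends on whether a profile happens to have a 48 h sample; and summaries headed as covering all participants that would contain mainly those who peaked early.

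**Working it through.** The documents give no expected ke or half-life that depends on this formula, so there is no figure to reproduce. The checks below apply the formula to noise-free curves at the scheduled times, with 5.5 h standing for 5-6 h.

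**1. Biphasic decline.** C(t) = 0.8·2^(−t/2) + 0.2·2^(−t/13.5). The 13.5 h is the top of the oral MIV-101 range in Protocol Table 8. The 2 h half-life, the 80% fast share and a peak at 3 h (so C1 is at 4 h) are assumptions. Time can be counted from dosing or from the peak, so both are shown.

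| Time zero | C(4 h) | C(24 h) | C(48 h) | t1/2, last sample 24 h | t1/2, last sample 48 h |
|---|---|---|---|---|---|
| Dosing | 0.3629 | 0.0585 | 0.0170 | ke = ln(0.3629/0.0585)/20 = 0.0912; 7.6 h | ke = ln(0.3629/0.0170)/44 = 0.0696; 10.0 h |
| 3 h peak | 0.7557 | 0.0686 | 0.0198 | ke = ln(0.7557/0.0686)/20 = 0.1200; 5.8 h | ke = ln(0.7557/0.0198)/44 = 0.0827; 8.4 h |

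Against a true 13.5 h, half-life is 44% to 57% too short with a last sample at 24 h and 26% to 38% too short at 48 h. The same participant would therefore show a longer half-life at whichever volume drew the 48 h visit.

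**2. Effect on AUC0-inf in that scenario.** AUC up to the last sample is taken as exact. With time from dosing, the total area is (0.8×2 + 0.2×13.5)/ln 2 = 6.20 and the true tail after 24 h is 1.14. The formula's tail is 0.0585/0.0912 = 0.64. AUC0-inf is then (5.07 + 0.64)/6.20 = 0.92 of true, and %AUCex is 11% instead of 18%. With time from the peak and an assumed linear rise to 3 h, AUC0-inf is 0.90 of true. With a 48 h sample it is 0.98 to 0.99.

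**3. Wider biphasic grid.** This used terminal half-lives of 10, 13.5 and 24 h, assumed distribution half-lives of 1.5 or 3 h, a terminal share of 0.1-0.5 and absorption rates of 1.0 or 1.5 per h. Half-life is 15% to 73% too short (24 h) or 7% to 56% too short (48 h). AUC0-inf is 0.75-0.97 of true (24 h) or 0.91-1.00 (48 h).

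**4. One-phase decline, 24 h sample quantifiable.** C(t) is proportional to 2^(−t/4.82) − exp(−ka·t). The 4.82 h is the vaginal run-in median in Protocol Section 2.5; ka is assumed.
- ka 0.7 (sampled peak 3 h): ln(0.5018/0.0317)/20 = 0.138; 5.0 h, +4%.
- ka 1.0 (sampled peak 2 h): ln(0.5998/0.0317)/21 = 0.140; 4.95 h, +3%.
- ka 1.5 (sampled peak 2 h): ln(0.6385/0.0317)/21 = 0.143; 4.85 h, +1%.

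The slowest absorption that still puts the sampled peak at 3 h (ka about 0.51) gives 5.3 h, +10%.

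**5. One-phase decline, 24 h sample BLOQ and treated as missing.** With ka 1.0, the values at 3, 4 and 5.5 h still satisfy the three-value rule. Then ke = ln(0.5998/0.4493)/2.5 = 0.116, or 6.0 h, +24%. With an assumed 20% error per value, the SD of ke is √2×0.2/2.5 = 0.113 against a true ke of ln 2/4.82 = 0.144, so near-zero or negative slopes are plausible. At the run-in Cmax of 84.7 pg/mL at 3.92 h, the expected 24 h value is 84.7×2^(−20.08/4.82) = 4.7 pg/mL. Without a stated LLOQ, one cannot say how often this case arises.

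**6. Who is evaluable.** Plasma samples left after the sampled peak:

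| Peak at | Without 48 h | With 48 h |
|---|---|---|
| 3 h | 3 | 4 |
| 4 h | 2 | 3 |
| 5-6 h | 1 | 2 |

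Only 12/3 = 4 profiles per volume have the 48 h sample. Vaginal-gel median Tmax was 3-5 h, with an overall range of 2-12 h (Protocol Section 2.5).

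**7. What regression changes.** In scenario 1, regression on the last three points gives 6.0-7.9 h (4, 5.5, 24 h) and 9.2-10.8 h (5.5, 24, 48 h). Only the 24-48 h slope comes close to the truth (13.4-13.5 h). In the one-phase case with 20% error and points at 4, 5.5 and 24 h, the SD of ke falls only from 0.0141 to 0.0127.

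**The case against.** A reader might infer that half-life and AUC0-inf will simply be biased low. The documents do not support that. Biphasic decline is described only after oral dosing. The vaginal-gel data, which are closer to this product, give median half-lives of 3.9-5.5 h with no second phase described, and Protocol Section 2.5 says there are no rectal data. With the vaginal half-life and a quantifiable 24 h sample the error is small (step 4). The SAP also says first value in the elimination phase, not first value after the peak, so an analyst has some latitude. All of this stands. The latitude is itself undefined, though, and the sentence introducing the formula speaks of concentrations after Cmax.

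A reader might also quote the tail alone, which in step 1 is 43% to 74% of the truth. The reported parameter is AUC0-inf, which moves by 10% or less in that scenario.

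The consequence is limited. The primary PK endpoint is concentrations, plasma parameters are optional, no formal testing is planned, and concentrations are listed by participant, so ke can be re-estimated. Cmax, tmax and AUC0-t do not use it. This argues against treating the point as critical, not against correcting it.

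Finally, regression gains little where no sample lies between 6 h and 24 h. That is true (step 7), and it is why the reporting rules matter at least as much as the change of estimator.

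**Conclusion.** The point holds as a defect of specification: ke is called terminal, needs three values, uses two, and rests on an undefined phase. The size and direction of the error depend on a rectal profile that nobody has yet seen. If decline is biphasic, half-life is too short (by 26% to 57% in the worked scenario, whose fast phase is assumed), AUC0-inf and %AUCex are too low, and the result depends on which volume had the 48 h visit. If decline is one-phase at the vaginal half-life, the error is about +1% to +5% with a quantifiable 24 h sample, somewhat more if absorption is slow. It can be large and upward if that sample is BLOQ.

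The selection problem needs no kinetic model. By 24 h, a peak at 4 h or later cannot meet the three-value rule, so the half-life and AUC0-inf tables would lean towards early peakers.

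On composite rectal curves, C1 is a mean or median of three people, and C2 comes from a different three at 24 h or a differently composed four at 48 h. For vaginal fluid, the stratification in SAP Section 2.3.1 gives only 1-2 women per time frame up to 24 h. Such a slope is not an elimination rate in anyone.

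This should be fixed before analysis; it does not threaten the primary endpoint.

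**What to change.** In SAP Section 9.2:

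- Replace the two-point formula with log-linear regression on at least three quantifiable post-Cmax points, chosen from the end of the profile and not forced to include the first post-peak sample.
- List the points used, a fit statistic and %AUCex for each profile, and flag poorly supported values. A good fit alone is not proof of a terminal slope.
- Report the number evaluable for t1/2 and AUC0-inf at each volume.
- Compare volumes on Cmax, tmax and AUC over a common 0-24 h window.
- Do not report ke, t1/2 or AUC0-inf from composite rectal or vaginal curves, or label them descriptive only.

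Two tempting additions are best left out. Restricting the slope to samples at 5 h or later would confine it to the one profile per participant with a 48 h sample. At vaginal exposure that sample is expected at 84.7×2^(−44.08/4.82) = 0.15 pg/mL and may not be quantifiable. Carrying one participant's slope across volumes assumes that decline does not depend on volume, which is untested.

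The cost is SAP wording, with fewer or flagged individual half-lives. When the peak is at 3 h and there is no 48 h sample, the three available points still include the first post-peak one. Regression does not remove the bias from having no plasma sample between 6 h and 24 h, and the report should say so.

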#### 10. SECONDARY ANALYSES

# 10.1 Acceptability Analyses

Enrolled participants are administered web-based self-interviews (WSI) at Enrollment (Visit 2) and at the three dosing visits (Visits 3, 5, and 7). The WSI at dosing visits explore reactions to product, with an emphasis on identification of product attributes likely to challenge and/or facilitate future sustained use when applied rectally by participants.

To address the secondary endpoints of participant self-report of comfort with gel application, liking the product across doses, and perceived side-effects, responses to WSI questions in section B (Rectal Gel Acceptability) and section C (Experiences Using the Product) of the dosing visits (Visits 3, 5, and 7) will be summarized in a table by dose/volume.

# 10.2 Secondary PK Analyses

The secondary PK analyses describe the analyses of MIV-150 concentrations in vaginal fluid and are limited to participants identified as female sex at birth.

For these secondary PK analyses, the primary PK analyses for rectal fluid and/or rectal tissue will be repeated for MIV-150 concentrations in vaginal fluid.

